16.7 Translational studies

All translational research will be exploratory and hypothesis generating due to the small sample size. We will correlate clinical data (i.e. response, OS, PFS, adverse events) with translational marker data (i.e. MMR/MSI, PDL1 expression, Cell free DNA, genetic sequencing data, blood markers, Bim levels, T cell markers, sPD-L1, total mutational burden, etc.). These correlations will be done using the Chi-square or Fisher's exact test for categorical data and Kaplan-Meier methods (including the log-rank test) for the survival endpoints. Univariate Cox regression models will also be done to assess for marker effects on survival endpoints. Descriptive statistics and graphical methods will be used to summarize the data as well. All these analyses will be done overall and by MMR/MSI status.

Genetic/genomic testing performed for clinical purposes will be requested for patients from the local sites, and will be deidentified for inclusion in analyses.

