2.3 Correlative Research

- 2.31 To determine whether PD-L1 expression, as measured by IHC, or MSI status is associated with the response rate overall.
- 2.32 To determine if Bim levels in tumor-reactive CD11ahighPD-1+CD8+ peripheral

blood T cells can objectively monitor responses to pembrolizumab and to determine if excessive release of soluble B7-H1 (sPD-L1) by the tumor leads to Bim upregulation and treatment resistance in SBA.

2.33 To determine if other tissue-based factors, such as total mutational burden, correlate with response to pembrolizumab.

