4.0 Test Schedule

Tests and procedures	Active Monitoring Phase			
	≤28 days prior to registration	Day 1 Cycle 1	Day 1 Cycles 2 -8 and beyond (+/-3 days)	End of treatment (PD, withdrawal, or removal ⁹) (+7days)
History and exam, wt, ECOG PS	X	X ^{6,8}	X ⁶	X
Height	X			
Adverse event assessment	X	X ⁸	X	X
Concomitant medication review	X	X ⁸	X	
Hematology: CBC/ differential	X	X	X	X
Chemistry: SGOT (AST), ALT, alk phos, T. bili, creatinine, calcium,, Na, K, glucose, LDH, bicarbonate, uric acid, Mg, Phosphorus, total protein, blood urea nitrogen, albumin	X	X	X	
PT/INR and aPTT	X			
Urinalysis ³	X			
T3, FT4 and TSH	X	X	X	
Tumor measurement (should include at least a CT of the abdomen/pelvis, and appropriate imaging of any other target site lesions) ^{1, 10}	X		X ⁵	X
CEA	X		X ⁷	X
Pregnancy test	X ²			
Mandatory blood sample (see Section 14.0) ⁸	X	X	X ⁴	X
Mandatory tissue sample (see Section 17.0)	X			

1. Use same imaging throughout the study.
2. For women of childbearing potential only. Must be done ≤7 days prior to registration.
3. Urine blood, glucose, protein, specific gravity. Microscopic exam if abnormalities on urinalysis results.
4. Collected cycles 2, 3, 4, 8 (see Section 14.0). Kits are required for this collection.
5. Every 4 cycles beginning with end of cycle 4, and at end of treatment.
6. Directed physical exam only.
7. Every even-numbered cycle, beginning with cycle 2, and at end of treatment.
8. ≤24 hours prior to treatment.
9. Continued study treatment beyond initial radiographic disease progression may be allowed; see Section 13.4 for details. These

patients would continue follow-up per test schedule until confirmed progression.

10. To be submitted <60 days after registration

R Research funded (see Section 19.0). Mandatory research blood draws should be collected and submitted *after* the patient is registered onto the study, but before beginning study treatment.

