16.6 Secondary endpoints

These endpoints include progression-free survival (PFS), overall survival (OS), and adverse events.

- Progression-free survival (PFS) is defined as the time from study entry to the first of either disease progression or death from any cause, where disease progression will be determined based on RECIST 1.1 criteria. PFS will be estimated using the Kaplan-Meier method.
- Overall survival (OS) is defined as the time from study entry to death from any cause. OS will be estimated using the Kaplan-Meier method.
- Adverse events: The maximum grade for each type of adverse event will be summarized using CTCAE version 4.03. The frequency and percentage of grade 3+ adverse events will be summarized.

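### Does Section 16.7 build immortal-time bias into the analyses of serial blood markers against PFS and OS?

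*Combined protocol and SAP*

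**What the plan says.** Section 16.7 correlates response, OS, PFS and adverse events with these markers: "MMR/MSI, PDL1 expression, Cell free DNA, genetic sequencing data, blood markers, Bim levels, T cell markers, sPD-L1, total mutational burden, etc". For time-to-event outcomes it names "Kaplan-Meier methods (including the log-rank test) for the survival endpoints", then adds: "Univariate Cox regression models will also be done to assess for marker effects on survival endpoints". It gives no sampling time, grouping rule, landmark or time-dependent covariate. It opens with the status of the work: "All translational research will be exploratory and hypothesis generating due to the small sample size".

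Section 16.6 sets the clock: "Progression-free survival (PFS) is defined as the time from study entry to the first of either disease progression or death from any cause", and "Overall survival (OS) is defined as the time from study entry to death from any cause".

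Section 4.0 schedules research blood before treatment, at cycle 1, at later cycles (footnote 4: "Collected cycles 2, 3, 4, 8 (see Section 14.0"), and at end of treatment. Section 14.1 agrees: baseline, cycles 1-4 and 8, and end of treatment. The MMR, PD-L1 and lymphocyte stains in Section 17.32 use baseline tumor tissue.

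Objective 2.32 deals with the Bim protein and reads in part: "blood T cells can objectively monitor responses to pembrolizumab and to determine if excessive release of soluble B7-H1 (sPD-L1) by the tumor leads to". The effects it goes on to name are a rise in Bim and failure of the drug. It therefore concerns response and resistance and names neither PFS nor OS.

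**The concern.** Three facts together look troublesome. The survival clock starts at entry, the marker may be measured weeks later, and sampling stops when treatment stops, which is usually at progression. A cycle 8 sample exists only for someone still on treatment at about week 21. A group defined by any high value during treatment therefore favors patients who last longer, and the log-rank test from entry credits that advantage to the marker.

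Objective 2.32 needs on-treatment values and Section 16.7 is the only analysis text that could cover them, so it is natural to assume that such values will enter these tests. At stake is a false lead on Bim or sPD-L1 carried into later studies. The exploratory label covers imprecision, not systematic error.

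Two further worries come with it. End-of-treatment samples are often drawn at progression. Section 16.7 also names tests for categorical markers against response, which could suggest that continuous markers must be cut into groups.

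**Working it through.** Section 16.7 states no power, event count or error rate, so there is no figure of the plan's own to reproduce on this point.

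**Inputs from the documents.** 35 evaluable patients (16.32); 21-day cycles (Schema); blood at cycles 1-4 and 8 (14.1); scans every 12 weeks (11.1); accrual of about 14 months and 12 months' follow-up of the last patient (16.5). **Assumed, not in the documents:** exponential event times with medians of 2 to 12 months; a marker unrelated to outcome; 30% of samples high; independent visits unless stated.

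**Sampling times.** Day 1 of cycle k falls at week 3(k − 1). Cycles 2, 3, 4 and 8 give weeks 3, 6, 9 and 21.

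**Where bias can arise.** With m independent samples, P(ever high) = 1 − 0.7^m.
- Event before week 3 (m = 1): 0.30
- Event between weeks 9 and 21 (m = 4): 1 − 0.7^4 = 0.76
- Still sampled at week 21 (m = 5): 1 − 0.7^5 = 0.83

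The bias comes from events in the first nine weeks. Radiographic progression is first scheduled to be seen at 4 × 3 = 12 weeks, after four of the five samples. From then on the contrast is only 0.76 against 0.83.

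**One visit's value.** Suppose only patients sampled at week 9 are compared and none has had a counted event by then. At every event time t the risk set is the sampled patients still under observation at t, whether the clock starts at entry or at week 9. The log-rank statistic and the Cox partial likelihood are then the same as in a landmark analysis.

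**Null simulation**, two-sided 5%, 2,000 trials per setting:

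| Handling of the noise marker | Rejection (%), median 2 / 4 / 6 / 12 months | Hazard ratio |
|---|---|---|
| Baseline value | 6.0 / 6.5 / 5.7 / 4.7 | 0.99-1.00 |
| Cycle 4 value, sampled patients only, from entry | 8.8 / 6.6 / 6.3 / 6.2 | 0.99-1.00 |
| Cycle 8 value, sampled patients only, from entry | 10.2 / 7.8 / 7.5 / 5.8 | 0.98-1.00 |
| Cycle 8 value, unsampled counted as low | 39.5 / 30.2 / 23.3 / 12.9 | 0.40-0.61 |
| Ever high, from entry | 53.8 / 40.5 / 31.3 / 23.4 | 0.43-0.59 |
| Ever high, time-dependent covariate | 5.2 / 5.0 / 5.3 / 6.0 | 0.97-1.00 |
| Ever high by week 9, landmark | 8.2 / 6.2 / 6.0 / 6.6 | 0.97-1.02 |

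The excess for the single-visit values is a small-sample effect, since the hazard ratio stays near 1. At a 2-month median, week 21 is 21 × 12/52 = 4.85 months, so about 35 × 0.5^(4.85/2) = 6.5 patients remain.

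**With events seen only at 12-weekly scans** (median 4 months), ever high falls from 40.5% to 11.3% (hazard ratio 0.84), and unsampled-as-low falls from 30.2% to 17.8% (0.60). For a grouping of ever above 1 SD on treatment, at medians of 2 to 6 months, rejection is 17-37% with exact event times and independent visits, or 8-20% with correlation 0.5 between visits. On the scan grid these become 6.8-8.3% and 5.4-6.9%.

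**Continuous markers.** A univariate Cox model takes a continuous covariate as it stands, so nothing in the survival analyses forces a cut. Only the comparison with response lacks a named continuous test. A Wilcoxon test is the routine choice there, and Section 16.7 already adds descriptive and graphical methods.

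**The case for a change.** The strongest case for acting runs as follows. The serial draws are mandatory and Section 16.7 is their only analysis text, so on-treatment values will be analyzed somehow. Leaving the time point open also allows it to be picked after the data are seen. Not every event waits for a scan: deaths, symptomatic deterioration (Section 11.45) and early withdrawal fall between scans, so the true inflation lies between the scan-grid and exact-time figures. A rule that looks harmless can fail too. The last on-treatment value rejects in 5-7% of trials when the marker is stable. If the marker rises in everyone by an assumed 1 SD by week 21, that becomes 16-23% with exact times and 9-20% on the scan grid. A few sentences would close the gap.

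Much of this is sound as advice to the analyst. Ever-high, unsampled-as-low and last-value groupings should not be run from entry. An end-of-treatment value should not be related to PFS either, although that error would be reverse causation rather than immortal time. What does not stand is the step from a silence to a fault. Section 16.7 prescribes none of these groupings, each blood marker has a valid pre-treatment value, and the objective that uses serial values is about response and resistance.

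**Conclusion.** No change to the plan follows. Section 16.7 leaves out which blood sample enters the survival analyses and how repeated values are handled. It permits a biased definition but does not specify one, and no rule it does state gives a wrong result. A competent analyst fills the gap in the ordinary way: baseline values from study entry, a single visit's value among those sampled then, and a landmark or time-dependent covariate for anything pooled over visits. In the simulations these gave about 5-10% rejection with hazard ratios of 0.97 to 1.02.

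The large figures, up to 54%, need a grouping the plan does not name together with many events before the first scan. On the 12-weekly scan grid the inflation was about 6-9% for ever above 1 SD and 11% for ever high at 30% prevalence.

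These sizes rest on assumed medians, marker prevalence and visit correlation, none of which is in the documents. The equality of single-visit and landmark analyses requires that no counted event precede the sample. That fits cycle 4, which comes before the first scheduled scan. For PFS at cycle 8, patients treated beyond first progression under Sections 7.6 and 13.4 would have to be left out.

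All of this work is declared exploratory, and none of it enters the decision rule of 7 or more confirmed responses in 35 (Section 16.32).

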It has recently been suggested that dMMR/MSI-H patients may have a superior response to anti-PD1 therapy. (Le, Uram et al. 2015) In our preclinical study, seven of the 50 tumors (14%) were already known clinically to be dMMR/MSI-H. These had a superior prognosis to tumors not known to be dMMR/MSI-H (median survival not reached vs 2.5 years, $p=0.028$ by Log-Rank), suggesting a unique biology at baseline and is in keeping with survival data on Lynch syndrome patients with cancer of the large intestine. While the response to PD-1 inhibitors was most prominent in the dMMR cohort of the Le et al. study (ORR 40%), a small number of patients with proficient MMR and microsatellite stability (pMMR/MSS) did achieve a small response or stable disease, indicating potential efficacy in both cohorts.

Our goal is to evaluate whether pembrolizumab administered to patients with advanced small bowel adenocarcinoma in second- or later lines of therapy demonstrates antitumor activity as measured by confirmed response rate. Secondary endpoints would include response in dMMR vs. pMMR patients, response in PD-L1 (+) vs. PD-L1 (-) expressers, progression-free survival (PFS), overall survival (OS), and tolerability.

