16.32 Final Analysis Decision Rule

Enter a total of 35 evaluable patients. If 6 or fewer of these 35 patients have a confirmed response, we will conclude that this treatment is insufficiently active in this population. If 7 or more of these 35 patients have a confirmed response (20%), this will be considered adequate evidence of efficacy of this treatment and may be recommended for further testing in subsequent studies.

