16.33 Sample Size and Power

We anticipate accruing an additional 5 patients to account for ineligibilities, cancellations, major violations, or other reasons. Therefore, maximum accrual is 41 patients. This design has a significance level of 0.06 when the confirmed response rate is 10%, and 94% power to detect a confirmed response rate of 30%.

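### Section 16.7 offers only unadjusted marker tests overall and within MMR/MSI groups; an MMR-stratified analysis and exact small-sample methods should be added, because the dMMR group will number about 5

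*Combined protocol and SAP*

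**What the plan says.** Section 16.7 relates response, PFS, OS and adverse events to an open-ended list of markers (MMR/MSI, PD-L1, cell-free DNA, Bim, T-cell markers, soluble PD-L1, mutational burden and others). The methods are these:

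- Response and other categorical outcomes are compared by chi-square or by Fisher's test; PFS and OS are compared by log-rank tests with Kaplan-Meier curves.
- Regression is limited to one marker at a time: "Univariate Cox regression models will also be done to assess for marker effects on survival endpoints".
- The whole set is then repeated by subgroup: "All these analyses will be done overall and by MMR/MSI status".

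The section does not say when chi-square and when Fisher applies. It sets no significance level and no minimum group size, and names no stratified or multivariable model. It states that all translational work is exploratory and hypothesis generating because the sample is small.

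The only dMMR prevalence in the document is in section 1.3: "seven of the 50 tumors (14%) were already known clinically to be dMMR/MSI-H". Section 16.32 sets the sample ("Enter a total of 35 evaluable patients") and section 16.33 the ceiling ("Therefore, maximum accrual is 41 patients"). Objective 2.31 asks whether PD-L1 or MSI status is associated with response overall. Objective 2.33 asks whether other tissue factors, such as mutational burden, correlate with response.

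**The concern.** MMR/MSI is the factor that the protocol itself links to outcome. Section 1.3 cites a 40% response rate to PD-1 blockade in dMMR tumours and reports better survival in the sponsor's own dMMR cases (p=0.028). The plan handles MMR only by splitting the sample or ignoring it, and three weaknesses follow.

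1. The dMMR subgroup is probably too small for p-values to mean much. One named response test cannot give a small p-value there, while the other, like the log-rank test, can give one too easily.
2. The asymptotic log-rank is also unreliable in the full sample when a marker is rare.
3. A marker that travels closely with MMR can appear to predict response overall when it has no effect within either MMR group.

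These analyses exist to generate hypotheses, so what is at stake is pursuing the wrong marker, or reading an uninformative subgroup result as negative. The primary decision on confirmed response does not depend on them.

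**Working it through.** **The plan's own figure.** Section 16.33 states: "This design has a significance level of 0.06 when the confirmed response rate is 10%, and 94% power". For the rule of 7 or more responders in 35, the exact binomial gives P(X≥7 | 10%) = 0.055 and P(X≥7 | 30%) = 0.935, which agree with the printed values after rounding. Section 16.7 gives no figure to reproduce.

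**Size of the dMMR group.** Expected number: 0.14 × 35 = 4.9 (0.14 × 41 = 5.7). With X ~ Binomial(N, 0.14):

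- P(X≤6) = 0.79 at N=35 and 0.65 at N=41, so 7 or more has probability 21% or 35%.
- The exact 95% interval for 7/50 is 5.8% to 26.7%, or 2.0 to 9.4 expected patients of 35.
- The 14% counts only tumours already known to be dMMR and may be low. At an assumed 20%, P(X≤6) = 0.43 at N=35. In the other direction, section 17.1 lets patients without tissue stay eligible, so fewer may be typed.

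**Response tests in that group (yes/no outcome).** Enumerating all tables, the smallest two-sided Fisher p is:

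- n=5: 1/C(5,2) = 1/10 = 0.10
- n=6: 1/C(6,2) = 1/15 = 0.067
- n=7: 1/C(7,3) = 1/35 = 0.029

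Uncorrected chi-square for a perfect 2-vs-3 split equals n = 5, giving p=0.025 where the exact p is 0.10. The same data look positive or negative depending on which listed test is used.

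**Log-rank with 5 or 6 patients.** Take 2 marker-positive and 3 marker-negative patients, with both positives failing first:

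- O = 2; E = 2/5 + 1/4 = 0.65
- V = (2/5)(3/5) + (1/4)(3/4) = 0.4275
- Chi-square = (2 − 0.65)²/0.4275 = 4.26, p=0.039; the exact p is 1/10.

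For 1 vs 4: (1 − 0.2)²/0.16 = 4.0, p=0.046; the exact p is 1/5.

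True size at nominal 5% without censoring, by full permutation: n=5, 10% (2 vs 3) and 20% (1 vs 4); n=6, 10% (3 vs 3), 13% (2 vs 4) and 17% (1 vs 5).

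Censoring changes this. For 2 vs 3, simulated size is about 8% to 10% when 20% to 50% are censored at a common cutoff. With random censoring it is about 6.5% at 20%, 4.9% at 30% and 2.3% at 50%. For 1 vs 4 with 30% random censoring it is still about 14%.

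**Log-rank overall, rare marker.** Section 1.3 reports tumour-cell PD-L1 staining in 8%. 0.08 × 35 = 2.8, about 3 vs 32. Simulated size is about 6% to 9% across the censoring patterns tried.

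**Confounding of the overall response test.** The simulated marker has no effect within either MMR group. Response is 40% in dMMR (section 1.3) and 0% to 10% in pMMR (assumed); N=35 with 14% dMMR. The marker frequencies are assumed, because the documents give none by MMR status.

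| Marker-positive, dMMR / pMMR | Overall Fisher rejects at 5% |
|---|---|
| 90% / 10% | about 18% to 40% |
| 80% / 20% | about 9% to 20% |
| 80% / 40% | about 4% to 5% |
| 42% / 42% | about 0.5% to 2% |

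At 90%/10%, the planned pMMR-only Fisher test rejects in 0% to 1.4%. An MMR-stratified exact test rejects in about 2% or less at both 90%/10% and 80%/20%.

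**Power.** Assume a marker in 50% of patients that raises response from 20% to 80% in dMMR and from 5% to 40% in pMMR. Power is about 70% for the overall test, 70% stratified, 55% to 58% within pMMR and 4% to 5% within dMMR. If the marker acts only in pMMR, the pMMR-only test has 56% and the stratified test 48%.

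**The case against.** The strongest reply is that section 16.7 already declares this work exploratory, sets no p<0.05 criterion, and plans descriptive and graphical summaries as well. That stands, and it limits the point to interpretation.

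Four stronger readings are tempting, and the documents do not support them.

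- *That the plan cannot answer 2.31 or 2.33.* Neither objective asks for an effect beyond MMR. Objective 2.31 asks about response overall, and the planned overall test answers it as written.
- *That the overall tests are confounded in general.* This needs a marker strongly associated with MMR. The documents report no such association, and at 80%/40% the false-positive rate is about nominal. The planned pMMR analysis, about 30 of 35 patients, is free of MMR confounding.
- *That the small-sample log-rank is always anti-conservative.* For 2 vs 3 the excess disappears at 30% or more random censoring, and with 4 uncensored patients the test can never reject. Section 1.3 reports that median survival was not reached in dMMR cases, so heavy OS censoring is plausible. On the other side, at least 12 months' follow-up before analysis (section 16.5) and up to 5 years in all (section 13.5) suggest mainly administrative censoring, under which the excess largely persists.
- *That one stratified test should replace the overall and by-MMR tests.* It gains no power over the overall test, loses some if the marker acts only in pMMR, and would hide any difference in marker effect between MMR groups.

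The Fisher limit is also conditional: it lifts if 7 or more dMMR patients are enrolled.

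**Conclusion.** The point holds as a gap in methods. Section 16.7 names no analysis that uses all patients while accounting for MMR, and no survival test that is valid in very small groups.

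If the dMMR share is near 14%, the dMMR group will most likely have 6 or fewer patients. Fisher's test then cannot reach two-sided p<0.05 for a yes/no outcome, while uncorrected chi-square and, depending on split and censoring, the log-rank test can overstate evidence (10% to 20% true size uncensored). The overall log-rank for a marker as rare as tumour-cell PD-L1 is mildly inflated, at about 6% to 9%. Confounding of the overall response test is serious only under strong marker-MMR association (18% to 40% at an assumed 90%/10%).

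These results rest on the 14% share, the assumed pMMR response of 0% to 10%, the assumed marker frequencies, and a two-sided 5% benchmark that the plan does not itself set. The primary conclusion is untouched. This is a low-priority but inexpensive improvement.

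**What to change.** Keep the overall and pMMR analyses, and add to section 16.7:

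- For each marker other than MMR/MSI, an analysis in all patients stratified by MMR/MSI: an exact stratified (Mantel-Haenszel type) test for response, and a stratified log-rank test and stratified Cox model for PFS and OS.
- Exact tests instead of chi-square whenever the table is sparse.
- Permutation p-values for any log-rank comparison, overall or within a subgroup, in which a group has fewer than about 6 patients.
- Descriptive reporting of the dMMR group (counts and exact intervals, no p-values) when it has 6 or fewer patients.

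The cost is SAP wording and slightly more analysis with standard software. Patients with unknown MMR/MSI need their own stratum or drop out of the stratified tests, and the plan should say which.
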